15.1.2 MANAGEMENT OF ANESTHESIA-RELATED COMPLICATIONS

(1) Anesthesia Drug Allergy: Prior to anesthesia, administer a small amount of drug spray to the throat. If a significant allergic reaction occurs, the anesthesia drug should not be used. For severe allergic reactions or cases of toxic side effects, symptomatic treatment should be administered immediately, such as using vasopressors. Atropine can be used for bradycardia, and immediate tracheostomy should be performed for cases of laryngeal edema causing airway obstruction. In cases of cardiac arrest, cardiopulmonary resuscitation should be initiated.

(2) Insufficient or Excessive Anesthesia Medication: Insufficient local anesthesia can cause coughing, vomiting, and discomfort in the subject, and increase the likelihood of injury during bronchoscopy. Excessive local anesthesia can increase the risk of cardiovascular and central nervous

system toxicity. The total dose of lidocaine for adults should be limited to 8.2 mg/kg, calculated based on a weight of 60 kg, and the dose of 2% lidocaine should not exceed 25 mL. Extra caution should be exercised for elderly subjects or those with impaired liver or heart function. When achieving the desired anesthetic effect, the amount of lidocaine injected through the bronchoscope should be minimized.

(3) Anesthesia Accidents: Life-threatening complications during bronchoscopy procedures are often related to preoperative medication and local anesthesia. The risk is further increased in elderly subjects or those with severe comorbidities such as cardiovascular disease, chronic lung disease, liver or kidney dysfunction, epilepsy, or other mental disorders. Mild sedation and analgesia using drugs to alleviate anxiety and increase the pain threshold can improve subject cooperation, expedite the procedure, and reduce harm to the subject. Short-acting benzodiazepines (such as midazolam) can induce anterograde amnesia and control hypertension, with a lower incidence of respiratory depression compared to propofol. Opioids (such as fentanyl) can raise the threshold for stimulus response and reduce the occurrence of reflex reactions. In the presence of underlying organ dysfunction, adjustments should be made to the doses of benzodiazepines, opioids, anticholinergics, and local anesthetics.

15.1.3 OTHER RISKS ASSOCIATED WITH BRONCHOSCOPY

15.1.3.1 Cardiac Arrhythmias

The most common is tachycardia accompanied by elevated blood pressure, often related to the stimulation and hypoxia caused by the bronchoscope. However, these are mostly self-limiting and quickly return to normal after the procedure is stopped. Severe and clinically significant arrhythmias and cardiac arrest are more common in individuals with pre-existing severe organic heart disease.

Insufficient anesthesia, passage of the bronchoscope beyond the vocal cords, intense stimulation of the tracheobronchial tree, and hypoxia are closely associated with cardiac arrhythmias. It is recommended to routinely monitor electrocardiography, blood pressure, and SaO₂ during bronchoscopy, and the bronchoscopy room should be equipped with resuscitation equipment.

15.1.3.2 Laryngospasm or Laryngeal Edema

These are commonly observed in subjects with difficult intubation or insufficient anesthesia, and in most cases, symptoms are relieved after removal of the

bronchoscope. However, upper airway injuries during the procedure can lead to life-threatening laryngospasm. Proficient bronchoscopy skills can reduce the incidence of laryngospasm.

Special attention should be given to subjects with pre-existing bronchospastic diseases, superior vena cava syndrome, or a history of angioedema. Severe cases of laryngospasm or laryngeal edema should be treated promptly with oxygen supplementation, antihistamines, or intravenous administration of glucocorticoids.

15.1.3.3 Severe Bronchospasm

This is commonly observed in subjects undergoing bronchoscopy during an acute exacerbation of bronchial asthma. The bronchoscope should be immediately removed, and appropriate treatment should be provided for the severe asthma attack. In general, bronchoscopy should be relatively contraindicated during an acute asthma exacerbation. If bronchoscopy is necessary due to the patient's condition, it is recommended to perform the procedure under general anesthesia and mechanical ventilation.

For this reason, subjects with asthma should be rigorously excluded before enrollment.

15.1.3.4 Postoperative Fever

Transient fever after bronchoscopy is common and generally does not require special treatment. However, if the fever persists and the chest X-ray shows progressive infiltrates, the subject should be treated with antibiotics.

The possibility of fever increases in elderly subjects and those with airway obstruction after bronchoscopic interventions.

For subjects with underlying valvular heart disease and risk factors for endocarditis, the American Heart Association recommends prophylactic antibiotic use during rigid bronchoscopy but not during flexible bronchoscopy. However, for subjects with a history of prosthetic valve replacement, surgical vascular shunts, or endocarditis, prophylactic antibiotic use is necessary.

15.1.3.5 Hypoxemia

Decreased arterial oxygen tension (PaO₂) during bronchoscopy is common. PaO₂ generally decreases by approximately 20 mm Hg (1 mm Hg = 0.133 kPa) during

bronchoscopy. Therefore, continuous monitoring of oxygen saturation (SaO₂) should be performed for all subjects undergoing bronchoscopy. If necessary, end-tidal carbon dioxide concentration should also be monitored. Routine oxygen supplementation should be provided during the procedure to maintain SaO₂ > 90%. Subjects with reduced lung function and sedation still require oxygen supplementation after the examination.

Bronchoscopy performed under local anesthesia with sedation can result in decreased oxygen saturation or inadequate ventilation, accompanied by a significant increase in PaCO₂. Subjects with underlying chronic lung diseases may experience severe hypoxemia, leading to cardiac arrhythmias and life-threatening situations.

15.1.3.6 Hemorrhage

Bleeding during or after bronchoscopy is common, but significant bleeding is uncommon.

Preoperative assessment for subjects at potential risk of bleeding: For certain subjects, such as those with uremia, immunosuppression, pulmonary arterial hypertension, liver disease, coagulation disorders, or

thrombocytopenia, the risk of bleeding is higher. Subjects without risk factors for bleeding before undergoing routine bronchoscopy do not require routine preoperative coagulation function screening. Conversely, for subjects at potential risk of bleeding, platelet count, prothrombin time, and activated partial thromboplastin time should be checked before bronchoscopy.

Currently, for subjects scheduled for bronchoscopic biopsy, it is recommended to perform platelet count, prothrombin time, and activated partial thromboplastin time tests prior to the examination. For subjects at risk of bleeding, even if biopsy is not performed and only routine bronchoscopy is conducted, platelet count and/or prothrombin time should be checked before the procedure. Long-term use of antiplatelet drugs such as clopidogrel should be discontinued for 1 week prior to biopsy. For subjects taking oral anticoagulants such as warfarin sodium, discontinuation of the medication for at least 3 days before the examination or administration of low-dose vitamin K antagonists should be considered. In rare cases where subjects must continue anticoagulant therapy, their

international normalized ratio should be reduced to <2.5 , and heparin should be used.

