6 SAFETY ASSESSMENTS

- Primary Endpoints:

Incidence and severity of cell therapy-related adverse events (AE) within 24 weeks post-treatment.

- Secondary Endpoints:

Incidence of complications during bronchoscopy within 24 weeks post-treatment;

Changes in pulmonary tumor markers compared to baseline at 12- and 24-weeks post-treatment;

Changes in abnormal values of routine safety checks compared to baseline within 24 weeks post-treatment (blood routine, urine routine, blood biochemistry and electrolytes, electrocardiogram).

Frequency and severity of acute IPF exacerbation events within 24 weeks post-treatment.

Corresponding indicators will be tested during follow-up observation, as follows.

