6.6 COMPLICATIONS OF BRONCHOSCOPY

Common complications of bronchoscopy include anesthesia accidents, bleeding, pneumothorax, laryngospasm, hypoxemia, infection, post-procedural fever, and other unforeseen events.

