8.2 SECONDARY OUTCOME MEASURES

- Incidence of complication related to bronchoscopy within 24 weeks after treatment.

- Changes in lung diffusing capacity for single-breath carbon monoxide (DLCO-sb) compared to baseline at 4-, 12-, and 24-weeks post-treatment.
- Changes in Forced Vital Capacity (FVC) compared to baseline at 4-, 12-, and 24-weeks post-treatment.
- Changes in the ratio of diffusing capacity for carbon monoxide/ the alveolar volume (DLCO/VA) compared to baseline at 4-, 12-, and 24-weeks post-treatment.
- Changes in 6-minute-walk test (6MWT) compared to baseline at 4-, 12-, and 24-weeks post-treatment.
- Changes in the St. George's Respiratory Questionnaire (SGRQ) scale compared to baseline at 4-, 12-, and 24-weeks post-treatment.
- Changes in imaging of lung by high-resolution computed tomography (HR-CT) compared to baseline at 24 weeks post-treatment.
- Frequency and severity of IPF exacerbation events within 24 weeks after treatment.
- Number of cases of participants with abnormal Blood routine results within 24 weeks post-treatment.
- Number of cases of participants with abnormal Urine routine results within 24 weeks post-treatment.

- Number of cases of participants with abnormal Blood biochemistry results within 24 weeks post-treatment.
- Number of cases of participants with abnormal 12-lead Electrocardiogram (ECG) results within 24 weeks post-treatment.
- Changes in tumor markers (Cytokeratin 19 fragment (CYFRA21-1), Neuron-specific enolase (NSE), Squamous cell carcinoma antigen (SCC), Carcinoembryonic antigen (CEA)) compared to baseline at 4-, 12-, and 24-weeks post-treatment.

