17.3.2 SAFETY EVALUATION

Adverse events (AEs) will be recorded after the first bronchoscopy collection and following the second bronchoscopy treatment. The description of AEs after the first bronchoscopy collection and the analysis of AEs after the second bronchoscopy treatment are as follows:

(1) Calculation of the incidence and severity of cell therapy-related adverse events (AEs) for each group.

(2) Calculation of the incidence of bronchoscopy-related complications for each group.

(3) Calculation of the mean, standard deviation, median, and interquartile range for the dynamic changes of each lung tumor biomarker in all groups.

(4) Presentation of the cross-tabulation of routine safety check abnormalities (complete blood count, urinalysis, blood biochemistry, electrolytes, electrocardiogram) between baseline and each visit.

(5) Recording the frequency and severity of acute IPF exacerbations

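### Bronchoscopy complications are defined and analysed as incidence only, without the severity given to the neighbouring safety items, so important procedure-related harm can be masked

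*Protocol*

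**What the plan says.** Three places in the protocol fix this endpoint, each time without severity:

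- Section 6: "Incidence of complications during bronchoscopy within 24 weeks post-treatment".
- Section 8.2: "Incidence of complication related to bronchoscopy within 24 weeks after treatment".
- Section 17.3.2, item 2: "Calculation of the incidence of bronchoscopy-related complications for each group".

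Item 1 of the same analysis list reads "Calculation of the incidence and severity of cell therapy-related adverse events (AEs) for each group", and item 5 asks for both frequency and severity of acute exacerbations.

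Section 6.6 gives the content of the endpoint, with no threshold for any entry: "Common complications of bronchoscopy include anesthesia accidents, bleeding, pneumothorax, laryngospasm, hypoxemia, infection, post-procedural fever, and other unforeseen events".

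Section 15.1.3 describes what is expected. On bleeding: "Bleeding during or after bronchoscopy is common, but significant bleeding is uncommon". On fever: "Transient fever after bronchoscopy is common and generally does not require special treatment". On oxygenation: "Decreased arterial oxygen tension (PaO₂) during bronchoscopy is common", with a usual fall of about 20 mm Hg and a warning that patients with chronic lung disease may become severely hypoxemic, to the point of danger to life. The opening of section 15.1, by contrast, puts the probability of complications in this study as very low.

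**The concern.** The listed complications range from events that the protocol expects and regards as mostly minor (bleeding, transient fever) to events that matter in any patient (anesthesia accident, pneumothorax). With no grade and no threshold, a patient with blood-streaked sputum and a patient with a major bleed add equally to the incidence.

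The severity analysis in item 1 may not catch the second patient, because it is limited to events related to the cell therapy. A serious bleed or pneumothorax put down to the bronchoscope would then appear only in item 2, ungraded. Safety and tolerability are the primary purpose of the trial (section 1), and every patient has two bronchoscopies, so the summary of procedural harm should separate the important from the expected.

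**Working it through.** **1. Does a graded summary elsewhere cover procedure-related events?** Section 11.4 judges causality against the investigational drug and classes an event with a clear alternative cause as definitely unrelated. A complication attributed to the bronchoscope can thus leave item 1 of section 17.3.2. That section lists no severity table for all adverse events. The grade itself is not lost: section 11.2 requires severity for every adverse medical event from the start of cell collection, and section 11.3 grades by CTCAE v5.0. What is missing is its use in this endpoint.

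**2. Group sizes.** Section 1.3 gives three groups of 3 to 6 and a fourth of 6: 3 + 3 + 3 + 6 = 15 and 6 + 6 + 6 + 6 = 24. This reproduces the 15 to 24 of section 17.1. The protocol states no complication rate, effect size or power for this endpoint.

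**3. How far an ungraded count can hide a difference.** Suppose item 2 is reported as one yes/no per patient over all complication types. Let m be the share of patients with a minor expected effect and s the share with an important complication, independent of each other. Then

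ungraded incidence = 1 − (1 − m)(1 − s),

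and between two groups the difference is (1 − m)(s₁ − s₀). The shrink factor is (1 − m).

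Assume s₀ = 5% and s₁ = 35%. Counting important complications alone, the difference is 30 points, or 0.3 against 2.1 expected patients of 6. Ungraded:

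| m (assumed) | 1 − (1 − m)(0.95) | 1 − (1 − m)(0.65) | Difference, points | Expected of 6 |
|---|---|---|---|---|
| 10% | 14.5% | 41.5% | 27 | 0.87 vs 2.49 |
| 30% | 33.5% | 54.5% | 21 | 2.01 vs 3.27 |
| 50% | 52.5% | 67.5% | 15 | 3.15 vs 4.05 |
| 70% | 71.5% | 80.5% | 9 | 4.29 vs 4.83 |
| 90% | 90.5% | 93.5% | 3 | 5.43 vs 5.61 |

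At m = 90% the measure saturates: all 6 patients of a group are cases with probability 0.905⁶ = 0.55 in the low-harm group and 0.935⁶ = 0.67 in the high-harm group.

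**4. Where m might lie.** With assumed rates of 20–50% for bleeding and 10–30% for fever, independent, m runs from 1 − 0.8 × 0.9 = 28% to 1 − 0.5 × 0.7 = 65%, so 72% down to 35% of the difference remains. Section 15.1's very low probability would put m near the top row of the table.

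**5. Would grading allow a formal comparison?** No. With s = 5% against 35%, a two-sided Fisher test at 0.05 has power 1.7% at 6 versus 6, even on the graded count (0 to 2.1% ungraded). With the first three groups pooled at their maximum, 18 versus 6, it has 29.9% graded and 22.6% down to 0.2% ungraded. The protocol plans descriptive statistics only.

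**The case against.** The strongest reply has four parts.

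- **Severity is already collected, and a table by grade is ordinary analysis-plan content.** The first half stands, and it is why the fix is cheap. The second half stands only in part: an analysis plan may add the table, but the protocol would still define the endpoint three times as incidence while naming severity for its neighbours.
- **Item 2 does not say that the incidence is a single composite per patient.** This stands. If incidence is reported by type, a pneumothorax or anesthesia accident is visible and masking between types disappears. Masking within a type, minor against major bleeding, remains.
- **Expected effects may never be counted.** Section 12.3 does not record laboratory abnormalities without clinical significance as adverse events, arterial blood gas is not scheduled at the bronchoscopy visits, and section 15.1 calls complications very unlikely. This stands as a reason why m may be small. It does not settle what counts, because section 6.6 sets no threshold and sections 15.1.3.4 to 15.1.3.6 call these effects common.
- **Harm by dose is decided elsewhere.** This stands. Section 1.6 stops escalation on graded related toxicity, related exacerbations and serious events, and on any event that the investigator and sponsor think sufficient.

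A reader might infer that the endpoint cannot show real harm by dose group, or that it is the only measure of harm from the delivery route. The documents support neither: grades and serious events are recorded throughout, exacerbations and ECG abnormalities are separate endpoints, and a post-instillation event judged possibly related enters the primary endpoint. Nor may all three expected effects be called trivial, since section 15.1.3.5 warns of severe hypoxemia. That warning is a further reason to grade.

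**Conclusion.** The point holds as a gap in the endpoint wording. Bronchoscopy complications are the one item among these three event endpoints defined without severity. The events concerned range from expected and minor to serious, and those attributed to the procedure can fall outside the cell therapy-related analysis. The result can mask important harm; it need not.

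The size is open. The factor (1 − m) is exact under independence and a single any-complication count, but m, the 5% and the 35% are assumptions. At m = 10%, 90% of a true difference survives (27 of 30 points); at m = 90%, 10% survives (3 of 30). No narrower range can be drawn from the protocol. The documents also give no ground for expecting complications to rise with dose; the two rates only show how the measure behaves.

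The benefit of grading is a clearer descriptive safety summary. It does not create a dose comparison, and it touches neither the primary endpoint nor the escalation rules.

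**What to change.** In sections 6, 8.2 and 17.3.2 item 2, replace incidence with *incidence and severity (CTCAE v5.0), by type of complication, for each group*. Show the collection and the treatment bronchoscopy separately: section 17.3.2 covers events after both, whereas the endpoint in sections 6 and 8.2 is timed from treatment. Use the grades already recorded under sections 11.2 and 11.3.

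Reconcile the very low probability in section 15.1 with sections 15.1.3.4 to 15.1.3.6, so that it is clear whether expected minor effects count as complications.

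A headline restricted to grade 2 or higher, or to events needing intervention, is not recommended. Oxygen is routine during the procedure (section 15.1.3.5) and section 5.1 calls for antibiotics when fever develops, so a needing-intervention count would again pick up expected effects; the documents give no basis for a grade 2 cut-off.

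The cost is one phrase in three sections, a clarification in section 15.1 and one table split. No new data are needed.

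### The pre-bronchoscopy text for subjects on warfarin offers a drug of warfarin's own class as the alternative to stopping it, and the sentence needs to be reconciled

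*Protocol*

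**What the plan says.** Section 15.1.3.6 (Hemorrhage) introduces its preparatory steps with "Preoperative assessment for subjects at potential risk of bleeding". Three instructions on antithrombotic drugs then follow in sequence:

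- Antiplatelet drugs: "Long-term use of antiplatelet drugs such as clopidogrel should be discontinued for 1 week prior to biopsy".
- Oral anticoagulants: "For subjects taking oral anticoagulants such as warfarin sodium", the text continues, "discontinuation of the medication for at least 3 days before the examination or administration of low-dose vitamin K antagonists should be considered".
- Subjects who cannot stop: "In rare cases where subjects must continue anticoagulant therapy", their "international normalized ratio should be reduced to <2.5", with heparin used.

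Section 6.6 names bleeding among the complications of bronchoscopy ("Common complications of bronchoscopy include anesthesia accidents, bleeding, pneumothorax"), and section 8.2 makes the incidence of such complications a secondary outcome. Section 1.4 places one bronchoscopy at the collection visit (V2) and another at transplantation (V4). Section 5.3 adds a repeat sampling if the first culture fails.

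**The concern.** The middle instruction joins two alternatives with an 'or', as if either would serve the same end. They do not point the same way. Stopping the drug lowers anticoagulation before the procedure. Giving a vitamin K antagonist, even at low dose, gives an anticoagulant of the class to which warfarin belongs. A site reading the sentence as printed cannot tell what is intended.

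What is at stake is the clarity of a patient-management instruction for an invasive procedure that every treated subject undergoes at least twice. The link to the trial's outcomes is that procedural bleeding counts in a secondary safety outcome. The point has no bearing on the statistical method.

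**Working it through.** No arithmetic applies. The only figures in the text (at least 3 days, 1 week, INR below 2.5) are stated rather than derived. The check is a side-by-side reading.

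1. **Who is covered.** Subjects on oral anticoagulants, with warfarin sodium as the example (section 15.1.3.6).

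2. **What the two branches do.** Branch A stops the drug for at least 3 days. Branch B administers a low-dose vitamin K antagonist. The one fact needed from outside the protocol is that warfarin is a vitamin K antagonist, which is a matter of drug-class definition. For a subject on warfarin, Branch B therefore gives the class that Branch A withdraws.

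3. **Fit with the sentence before.** For antiplatelet drugs the text offers withdrawal only, with no same-class alternative.

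4. **Fit with the sentence after.** Continued anticoagulation is presented as rare and carries its own INR condition. If giving a vitamin K antagonist were an ordinary option for any subject on warfarin, with no INR condition attached, it is hard to see what the exception would be an exception to.

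5. **Could 'low-dose' mean stepping warfarin down?** The text speaks of administration, not of reducing a dose, and subjects who remain anticoagulated already have their own sentence. The reading is possible but fits poorly.

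6. **Is the phrase explained elsewhere?** No. Section 3.4 (Concomitant Medication) has no anticoagulant rule, and section 5.1 (the bronchoscopy procedure) does not mention the subject.

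7. **Can it apply to enrolled subjects?** Yes. Section 2.3 does not list anticoagulant use. It removes two common reasons for it, pulmonary embolism (criterion 8) and atrial fibrillation on ECG (criterion 13), but not all: section 15.1.3.4 itself allows for subjects with a prosthetic valve.

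**The case against.** The best case for leaving the text alone has four parts.

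- **It looks like a wording or translation slip.** The surrounding instructions make the purpose plain, and a clinician would recognise the oddity. That is probably so, but this is the text sites hold, and section 18.2.3 does not let investigators depart from the protocol without sponsor consent and ethics approval, except to avert immediate harm or for administrative changes.
- **It is permissive and sits in a chapter on potential risks.** The alternatives are only to be considered. This softens the point. It does not remove it, because the sentence still tells sites how to prepare a subject.
- **Other checks exist.** Section 5.1 calls for review of history, CT and laboratory tests before bronchoscopy. Section 15.1.3.6 asks for platelet and/or prothrombin-time checks in subjects at bleeding risk. The flowchart notes list INR and APTT among the trial tests, and the investigator may exclude anyone judged unsuitable. These make harm less likely but do not clarify the phrase.
- **Few subjects are exposed.** Sampling is by brush (section 3.2.1), with biopsy only where new growths are seen (section 5.1), and two common indications for anticoagulants are excluded. This stands.

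A reader might also infer more than the documents support:

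- **That the sentence flatly contradicts the INR rule.** It does not. The INR condition is written only for subjects who must continue anticoagulation. An aim of lowering INR is explicit for them and at most implied for the rest. The concern with bleeding covers everyone at risk of it.
- **That a resulting bleed would distort dose escalation.** Section 1.6 requires the same or similar product-related events in two or more patients of a dose group, or a serious event judged related to the product. Section 11.4 requires other explanations to be weighed, and bleeding has its own place as a procedural complication. Misattribution is possible, but nothing in the documents makes it likely.
- **That a number of affected subjects can be given.** The documents supply no figure for anticoagulant use.

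**Conclusion.** The point holds as an internal inconsistency in a clinical-management sentence. For a subject on warfarin, the two alternatives work against each other, in a paragraph on bleeding risk, and the second sits badly beside the exception that follows.

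Its reach is one sentence, applicable to any anticoagulated subject at the two planned bronchoscopies and at any repeat sampling. The number is unknown and likely to be small. That expectation is an assumption resting on the exclusion of atrial fibrillation and pulmonary embolism. The conclusion otherwise rests only on the printed wording and on warfarin's drug class. The analysis, the sample size of 15 to 24 and all error rates are unaffected. The reason to act is that the text concerns safety and is easy to correct.

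**What to change.** The sponsor's responsible clinicians should check the vitamin K antagonist phrase, including against the source-language text, and establish what was meant. They should then reconcile the sentence with the purpose of its paragraph and with the INR sentence that follows, and issue the corrected sentence to all sites. Which drug, dose or rule belongs there is for them to decide; none is proposed here.

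The cost is a one-sentence protocol correction, the ethics committee review that section 18.2.3 requires for a protocol change, and a notice to sites. No visit, data item or analysis changes.
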